5.1.1. Level of Significance

The primary objective is to establish antiviral activity of JNJ-53718678. The primary efficacy endpoint is the RSV RNA viral load AUC from immediately prior to first dose of study drug through Day 5 ($AUC_{Day\ 5}$) derived from the RSV RNA viral load as measured by a qRT-PCR assay in nasal swabs. A hybrid methodology that combines aspects of multiple testing with modeling techniques (MCP-Mod) will be used for evaluating dose-

response trends and estimating the dose-response relationships. The dose-response will be tested at each (interim) analysis at alpha=2.5% (1-sided).

The primary analysis will only adjust for multiplicity with respect to the candidate models included into the MCP-Mod test. Due to the exploratory nature of the study, no adjustment for multiplicity due to sub-populations and adaptations will be considered in the primary analysis. A secondary analysis approach will be performed to control for multiplicity in the clinical course endpoints and for adaptations (see Section [5.2.3.2](#)).

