5.2.3.2. Methods to Control the Type I Error for Multiplicity and Adaptations

Due to the adaptive design, and multiple populations (i.e. full ITT-i analysis set and sub-population based on ITT-i subjects with symptom onset [≤ 3 days relative to randomization]), the Type I error will be controlled using the inverse-normal p-value-combination test as a secondary analysis approach. The total study alpha will be used at the timepoint for the primary analyses which are:

[figure not shown]
- Interim analysis 4 for antiviral effects ($\alpha=5\%$, i.e. 2.5% 1-sided)
- Final analysis for clinical course endpoints ($\alpha=20\%$, i.e. 10% 1-sided)

In a sequential testing framework, this corresponds to the following cumulative α -spending on primary and secondary endpoints:

	IA#1	IA#2	IA# 3	IA#4	Final Analysis
Viral load	0%	0%	0%	5%	5%
Clinical course	0%	0%	0%	0%	20%

This testing procedure will be applied on the ITT-i set

The primary endpoint on viral load ($AUC_{Day\ 5}$) will be tested at alpha of 5% (i.e. 2.5% 1-sided). To account for multiplicity in the statistical evaluation of the key clinical course secondary endpoints, a Bonferroni-Holm procedure will be applied to control for the overall Type I error rate. Clinical course endpoints are tested using an MCP-Mod test at 1-sided alpha level of 10%. Testing of the key clinical course endpoints (time to resolution of key RSV symptoms [ObsRO], incidence of RSV-related complications and change from baseline in key RSV symptoms [ObsRO]) will therefore be started at the 20/3 (6.667)% level. Levels used for testing will be adjusted, in case at least one of the key clinical course endpoints succeeds. The testing strategy is graphically summarized as:

The family wise error rate is strictly controlled at a level below 20% using the considered Bonferroni-Holm procedure.

The study design allows for enrichment at interim analyses 2, 3 and 4. The sample size re-estimation for clinical course endpoints will be conducted at interim analysis 3 only. To control for the multiple potential adaptations (enrichment and sample size re-estimation), the following procedures will be applied. All computations are to be conducted using stage-wise **1-sided** p-values. The final test decision is based on 2-sided p-values. Given the final 1-sided p-value, the 2-sided p-value results as:

- $p_{2\text{-sided}} = 2 \times \min\{p_{\text{reported}}, 1 - p_{\text{reported}}\}$

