- The conditional power at IA#4 is $<50\%$ to demonstrate antiviral activity of JNJ-53718678 compared with placebo based on the MCP-Mod trend test on viral load at 1-sided alpha=2.5% based on combined data from Cohort 1 and Cohort 2.

AND

- 80% 2-sided confidence interval on at least 2 key clinical course endpoints excludes effects as good as the TV based on data from Cohort 2 only

AND

- None of the 80% 2-sided confidence intervals on any key clinical course endpoint excludes effects as bad as the MAV based on data from Cohort 2 only

For viral load, the conditional probability of success at IA#4 using combined data from Cohorts 1 and 2 will be calculated assuming i) no enrichment and ii) enrichment as described below.

In both cases, the conditional probability of success will be set to 1 if the 1-sided p-value for the MCP-Mod trend test is less than 2.5% at IA#3, as success has already been reached. Otherwise, the conditional Type I error will be calculated using the inverse-normal combination approach:

$$\rho = 1 - \Phi \left(\frac{\Phi^{-1}(0.975) - \sqrt{w_1} \Phi^{-1}(1 - p_{Full})}{\sqrt{1 - w_1}} \right)$$

where:

- p_{Full} represents the 1-sided p-value for the MCP-Mod trend test for the full population at IA#3
- $w_1 = n_1 / n$
- n_1 represents the total number of randomized patients in Cohorts 1 and 2 at the time of IA#3
- $n = 294$, the planned total number of randomized patients in Cohorts 1 and 2 at IA#4

Given the conditional Type I error, the critical value for the MCP-Mod test based on new data from IA#4 only will be calculated. The conditional probability of success at IA#4 will be calculated under the observed test statistic at IA#3 (Z_1), adjusted for the sample size of the new data at IA#4 as:

$$CP_x = 1 - P(\bigcap_{i=1}^3 \{Z_{i,2} \in (-\infty, CRV)\})$$

where:

$$Z_2 \sim N \left(\mu_{Z,2} = \sqrt{\frac{n_2}{n_{1,x}}} Z_{1,x}, corr = corr_{MCPx} \right)$$

and:

- x corresponds to the decision not to enrich / to enrich at IA#3
- $Z_{1,x}$ represents the vector of observed MCP-Mod test statistics at IA#3 (Linear, Emax and Exponential models) based on the population of interest (full population for no enrichment and the sub-population with symptom onset ≤ 3 days for enrichment).
- Z_2 represents the vector of observed MCP-Mod test statistics for the second stage.
- $Z_{i,2}$ represents the observed MCP-Mod test statistic for the second stage (based on the new data at IA#4) for model i.

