- $Z_{x2;TV}$ represents the test statistic to test the null hypothesis that the difference between the high dose and the placebo treatment group is at least as good as the target value (TV) at the end of the study (full population for no enrichment and sub population with symptom onset ≤ 3 days for enrichment).
- $Z_{x2;MAV}$ represents the test statistic to test the null hypothesis that the difference between the high dose and the placebo treatment group is no better than the minimum acceptable value (MAV) at the end of the study (full population for no enrichment and sub population with symptom onset ≤ 3 days for enrichment).

For all clinical course endpoints, the conditional probability of an inconclusive result will then be calculated as:

$$CP_{x;Inconclusive} = 1 - CP_{x;Stop} - CP_{x;Go}$$

Interim analysis 4

The IDMC will consider stopping the study for futility, if:

- Viral load did not meet success based on the MCP-Mod trend test at 1-sided alpha=2.5% based on combined data from Cohort 1 and Cohort 2

AND

- 80% 2-sided confidence interval on at least 2 key clinical course endpoints excludes effects as good as the TV based on data from Cohort 2 only

AND

[figure not shown]
- None of the 80% 2-sided confidence intervals on any key clinical course endpoints excludes effects as bad as the MAV based on data from Cohort 2 only

For IA#3 and IA#4 two separate tests for two study populations are conducted and no formal multiplicity adjustments for the multiple study populations were implemented.

- Test for full population
- Test for subpopulation of patients ≤ 3 days since symptom onset

The futility rules defined are applied to each population separately. For decision-making, results of both populations will be considered. The following figure (refer to [Figure 3: Decision Flowchart](#)) provides an overview of the decision rules based on different endpoints to determine whether to stop the study for futility. Study will be stopped for futility if futility is reached in both populations.

Figure 3: Decision Flowchart

TV- Target value; MAV -Minimum Acceptable Value

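### The secondary analysis claims Type I error control over two populations, but states no rule linking the global and sub-population p-values

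*SAP*

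**What the plan says.** SAP section 5.1.1 leaves the primary analysis unadjusted for sub-populations and adaptations because the study is exploratory, and refers to section 5.2.3.2 for a secondary approach that does control error.

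Section 5.2.3.2 gives its reason as "Due to the adaptive design, and multiple populations (i.e. full ITT-i analysis set and sub-population based on ITT-i subjects with symptom onset" of at most 3 days, and continues: "the Type I error will be controlled using the inverse-normal p-value-combination test as a secondary analysis approach". It allots viral load 2.5% one-sided at IA#4, and the clinical endpoints 20% two-sided (10% one-sided) at the final analysis. The spending table shows 0% for viral load at IA#1 to IA#3. Holm starts at 20/3 = 6.667% for the three key clinical endpoints, and that paragraph closes with "The family wise error rate is strictly controlled at a level below 20% using the considered Bonferroni-Holm procedure".

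The tables that follow define a global and a sub final p-value for every scenario. For viral load without enrichment these are simply the full-population and sub-population MCP-Mod p-values.

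Section 5.6, on IA#3, says the conditional probability of viral-load success "will be set to 1 if the 1-sided p-value for the MCP-Mod trend test is less than 2.5% at IA#3", on the ground that success has by then been achieved. Section 5.1.1 says: "The dose-response will be tested at each (interim) analysis at alpha=2.5% (1-sided").

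**The concern.** Inverse-normal combination with preset weights keeps a p-value valid when the design changes between stages. It does not correct for testing two hypotheses. Holm, started at one third of alpha, allows for three tests; three endpoints in two populations make six. The text names multiple populations as something to be controlled, yet gives no order, closed-test condition or alpha split between the global and sub p-values. A reader of the final report could take a significant sub-population p-value as protected at 2.5%, or within the 20% family, when the text does not secure that.

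The IA#3 rule raises a smaller issue. With no alpha spent before IA#4, significance at IA#3 cannot be success under this approach, and replacing conditional power by 1 could alter the enrichment or futility guidance.

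**Working it through.** **Inputs.** Section 5.2.3.2: viral load 2.5% one-sided; clinical family 20% two-sided; viral-load N = 294, with about 75 + 36 = 111 subjects at IA#2 and 144 + 75 = 219 at IA#3; clinical weight 75/225 = 1/3 at IA#3. Section 1.2: ≤3-day share at least 45%. Assumed: share 45-55%, endpoint correlation as stated, and each MCP-Mod p-value treated as one valid p-value.

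**1. The plan's own figure.** Under the global null, Holm errs when the smallest of three p-values is at or below 6.667%. The Bonferroni bound is 3 × 6.667% = 20%. With independent endpoints the rate is 1 − (1 − 0.0667)³ = 18.7%; simulation with correlation 0.5 gives 16.4%. The statement is right for three endpoints in one population.

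**2. Viral load, two populations.** Without enrichment the full and sub statistics have correlation √share. The error is P(max > 1.96) for a bivariate normal:

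| ≤3-day share | Correlation | One-sided error |
|---|---|---|
| 45% | 0.671 | 4.2% |
| 50% | 0.707 | 4.2% |
| 55% | 0.742 | 4.1% |

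After enrichment both p-values share the second stage, so the correlation is w₁√share + (1 − w₁). For IA#3, w₁ = 219/294 = 0.745 and the error is 3.9-4.0%. For IA#2, w₁ = 111/294 = 0.378 and it is 3.5-3.6%.

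**3. Clinical family, two populations.** Each two-sided test at 6.667% has critical value 1.834. Simulation (2,000,000 draws), 50% share, no enrichment:

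| Endpoint correlation | One population, two-sided | Both, two-sided | Both, favourable direction (nominal 10%) |
|---|---|---|---|
| 0 | 18.7% | 29.3% | 15.5% |
| 0.5 | 16.4% | 25.8% | 13.0% |

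With enrichment at IA#3, shares 45-55% and correlations 0 to 0.6, the two-sided rate is 20.4-25.5%.

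**4. The IA#3 shortcut.** In single-statistic form, section 5.6 gives CP = 1 − Φ(crit − μ), with crit = (1.96 − √w₁·Z_full)/√(1 − w₁), μ = √(n₂/n₁)·Z for the population concerned, and n₂ = 294 − 219 = 75.

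- Full population at p = 0.025: crit = (1.96 − 0.863 × 1.96)/0.505 = 0.531; μ = √(75/219) × 1.96 = 1.147; CP = Φ(0.616) = 73%. This is below 100% but already above the 50% threshold.
- Enrichment calculation, sub-population just significant (Z = 1.96), 50% share, so n₁ = 109.5 and μ = √(75/109.5) × 1.96 = 1.622. With Z_full = 0.5, crit = 3.026 and CP = 8%. With Z_full = 1.0, crit = 2.172 and CP = 29%.

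The rule applies to both calculations and does not name the population whose p-value is meant. If it is the sub-population's in the enrichment case, the shortcut turns 8-29% into 100% and crosses 50%.

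**5. Would a simple gate suffice?** Suppose each sub test runs at its endpoint's Holm level once the global test rejects, while Holm also passes that level on. Take independent endpoints, with large effects confined to >3-day subjects so that the affected global tests reject.

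- Effect on one endpoint: 1 − (1 − 0.0667)(0.9)(0.9) = 24%.
- Effect on all three: 1 − (1 − 0.0667)(0.9)(0.8) = 33%.

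Both exceed 20%, because the alpha is used twice.

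**The case against.** The strongest reply is that the parts of a valid procedure are present. After enrichment the global p-value combines full-population stage-1 data with sub-population stage-2 data, which is the usual form of an intersection test. Read that way, with both p-values required for a sub-population claim, viral-load error returns to 2.5%. This stands as a reading, but the surviving text never states it. The testing-strategy graphic is not shown, so a gate drawn there cannot be excluded; the text around it mentions only the three endpoints.

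Three stronger readings are tempting and not supported:

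- A reader might infer that the Holm sentence is false. It is correct for the family its paragraph describes.
- A reader might infer that the primary analysis makes a broken promise. Section 5.1.1 openly declines adjustment there. Likewise, the section 5.6 remark that "no formal multiplicity adjustments for the multiple study populations were implemented" belongs to interim guidance, where the study stops only if both populations are futile; it does not describe the final p-values.
- A reader might infer repeated-look inflation, such as 3.7% if p < 2.5% counted at IA#3 or IA#4. No efficacy stop is planned, section 5.2.3.2 places the viral-load test at IA#4, and the sentence about testing at every analysis belongs to the unadjusted primary approach.

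**Conclusion.** The point holds for the secondary approach only. Section 5.2.3.2 claims control over two populations, and the methods it states do not supply it. The error rates in steps 2 and 3 arise if either p-value may support a claim, a use the text neither states nor excludes. They rest on the assumed ≤3-day share and endpoint correlations. The two-sided clinical figures include rejections in the wrong direction; counting favourable ones only, the excess is 13-16% against 10%.

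The IA#3 success wording contradicts the 0% spending row, but it is a wording and decision-rule inconsistency. It cannot move the full-population conditional power across 50%. It can do so for the ≤3-day enrichment calculation.

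**What to change.** In section 5.2.3.2, state that the global p-value is the intersection test, that a sub-population claim needs both the global and the sub p-value to be significant, and that after enrichment the global p-value alone supports no full-population claim.

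For the clinical endpoints, release an endpoint's Holm share to the others only after both its global and its sub test reject; this avoids the double use in step 5. Alternatively, limit the strict-control statement to the full-population family and label sub-population p-values as unadjusted.

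State that viral-load success under this approach is declared only at IA#4, or at the final analysis if the two coincide. In section 5.6, replace the rule that sets conditional probability to 1 with the formula value.

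The cost is a short text amendment, slightly fewer sub-population claims, and less alpha recycled across endpoints. No change to sample size or data collection is needed.

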Let the cumulative sample sizes for Cohort i up to analysis j be defined as n_{ij} :

	IA#1	IA#2	IA#3	IA#4	Final Analysis
Cohort 1 (n=144)	n_{11} (~36)	n_{12} (~75)	n_{13} (~144)	n_{14} (~144)	n_{15} (~144)
Cohort 2 (n=150)		n_{22} (~36)	n_{23} (~75)	n_{24} (~150)	n_{25} (~300)

RSV RNA Viral Load:

The total sample size planned for the primary analysis on viral load is given as: $n_{\text{Primary}}=294$. This constitutes the sample size of both Cohorts 1 and 2.

Stagewise weights and 1-sided p-values are defined as:

	IA#2	IA#3	IA#4
No enrichment:			
Weight	1		
p-value	p_{14}^F		
Final p-value (global)	p_{14}^F		
Final p-value (sub)	p_{14}^S		
Enrich at IA#2:			
Weight (w_{ij})	$(n_{12}+n_{22})/n_{\text{Primary}}$	$(n_{\text{Primary}} - n_{12} - n_{22})/n_{\text{Primary}}$	
p-value	p_{12}^F	p_{34}^S	
Final p-value (global)	$1 - \Phi \left(\sqrt{w_{12}} \Phi^{-1}(1 - p_{12}^F) + \sqrt{w_{34}} \Phi^{-1}(1 - p_{34}^S) \right)$		

	IA#2	IA#3	IA#4
Final p-value (sub)	$1 - \Phi \left(\sqrt{w_{12}} \Phi^{-1}(1 - p_{12}^S) + \sqrt{w_{34}} \Phi^{-1}(1 - p_{34}^S) \right)$		
Enrich at IA#3:			
Weight (w_{ij})	$(n_{13}+n_{23})/n_{Primary}$	$(n_{Primary}-n_{13}-n_{23})/n_{Primary}$	
p-value	p_{13}^F	p_{44}^S	
Final p-value (global)		$1 - \Phi \left(\sqrt{w_{13}} \Phi^{-1}(1 - p_{13}^F) + \sqrt{w_{44}} \Phi^{-1}(1 - p_{44}^S) \right)$	
Final p-value (sub)		$1 - \Phi \left(\sqrt{w_{13}} \Phi^{-1}(1 - p_{13}^S) + \sqrt{w_{44}} \Phi^{-1}(1 - p_{44}^S) \right)$	

- p_{ij}^F defines the p-value for the MCP-Mod test for data collected from in stages i to j in the full population
- p_{ij}^S defines the p-value for the MCP-Mod test for data collected from in stages i to j in the sub population

A p-value combination for the test of the sub-population is required, as the enrichment decision implies a sample size re-calculation for the sub-population.

Clinical Course Endpoints:

Sample size for clinical course endpoints is only based on Cohort 2. Let $n_{Primary} = 225$ be defined as midway between planned ($N= 150$) and maximum sample size ($N=300$).

	IA#2	IA#3	IA#4	Final Analysis
No enrichment:				
Weight (w_{ij})	$(n_{23})/n_{Primary}$		$(n_{Primary}-n_{23})/n_{Primary}$	
p-value	p_{23}^F		p_{45}^F	
Final p-value (global)	$1 - \Phi \left(\sqrt{w_{23}} \Phi^{-1}(1 - p_{23}^F) + \sqrt{w_{45}} \Phi^{-1}(1 - p_{45}^F) \right)$			

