Final p-value (sub)	$1 - \Phi \left(\sqrt{w_{23}} \Phi^{-1}(1 - p_{23}^S) + \sqrt{w_{45}} \Phi^{-1}(1 - p_{45}^S) \right)$			
Enrich at IA#2:				
Weight (w_{ij})	$n_{22}/n_{Primary}$	$(1-w_{22})* (n_{23}-n_{22})/(n_{Primary}-22)$		$(1-w_{22})* [(n_{Primary}-n_{23})/(n_{Primary}-n_{22})]$
p-value	p_{22}^F	p_{33}^S	p_{45}^S	
Final p-value (global)	$1 - \Phi \left(\sqrt{w_{22}} \Phi^{-1}(1 - p_{22}^F) + \sqrt{w_{33}} \Phi^{-1}(1 - p_{33}^S) + \sqrt{w_{45}} \Phi^{-1}(1 - p_{45}^S) \right)$			
Final p-value (sub)	$1 - \Phi \left(\sqrt{w_{22}} \Phi^{-1}(1 - p_{22}^S) + \sqrt{w_{33}} \Phi^{-1}(1 - p_{33}^S) + \sqrt{w_{45}} \Phi^{-1}(1 - p_{45}^S) \right)$			
Enrich at IA#3:				
Weight (w_{ij})	$n_{23}/n_{Primary}$		$(n_{Primary}-n_{23})/n_{Primary}$	
p-value	p_{23}^F		p_{45}^S	
Final p-value (global)	$\sqrt{w_{23}} \Phi^{-1}(1 - p_{23}^F) + \sqrt{w_{45}} \Phi^{-1}(1 - p_{45}^S)$			
Final p-value (sub)	$\sqrt{w_{23}} \Phi^{-1}(1 - p_{23}^S) + \sqrt{w_{45}} \Phi^{-1}(1 - p_{45}^S)$			

	IA#2	IA#3	IA#4	Final Analysis
Enrich at IA#4:				
Weight (w_{ij}) ^{\$}	$n_{23}/n_{\text{Primary}}$	$(1-w_{23})*(n_{24}-n_{23})/(n_{25,\text{Replan}}-n_{23})$	$(1-w_{13})*(n_{25,\text{Replan}}-n_{24})/(n_{25,\text{Replan}}-n_{23})$	
p-value	p_{23}^F	p_{44}^F		p_{55}^S
Final p-value (global)		$1 - \Phi \left(\sqrt{w_{23}} \Phi^{-1}(1 - p_{23}^F) + \sqrt{w_{44}} \Phi^{-1}(1 - p_{44}^F) + \sqrt{w_{55}} \Phi^{-1}(1 - p_{55}^S) \right)$		
Final p-value (sub)		$1 - \Phi \left(\sqrt{w_{23}} \Phi^{-1}(1 - p_{23}^S) + \sqrt{w_{44}} \Phi^{-1}(1 - p_{44}^S) + \sqrt{w_{55}} \Phi^{-1}(1 - p_{55}^S) \right)$		

\$ The denominator changes as we have the new sample size. The planned sample size is covered in w_{23} and $(1-w_{23})$. If study continues, the two new portions are identified as total n_{25} and (replan- n_{23}) subjects.

In case of no sample size increase, the IA#4 will coincide with the final analysis. In this situation, no enrichment at IA#4 is possible, such that either “no enrichment”, “enrich at IA#2” or “enrich at IA#3” will apply with p-values defined therein.

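### Two formulas in the clinical-endpoint combination-test table are wrong as printed (a missing 1 − Φ at IA#3, a wrong weight subscript at IA#4), and the Holm step states no direction for success

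*SAP*

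**What the plan says.** All of this is in SAP Section 5.2.3.2.

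- **Levels.** The clinical course endpoints carry 20% two-sided, equivalent to 10% one-sided. "Clinical course endpoints are tested using an MCP-Mod test at 1-sided alpha level of 10" per cent. Holm testing of the three key endpoints "will therefore be started at the 20/3 (6.667)% level". Once any of them is a success, the remaining thresholds change; no direction is attached to that condition.
- **Decision.** Stage-wise calculations are one-sided, but "The final test decision is based on 2-sided p-values", obtained as 2 × min{p, 1 − p}.
- **Weights.** n_Primary for the clinical endpoints is 225, midway between 150 and 300.
- ***No enrichment*, *Enrich at IA#2*, *Enrich at IA#4*.** The final p-values have the form 1 − Φ(weighted sum of normal quantiles).
- ***Enrich at IA#3*.** The global and the sub-population final p-values are printed as the weighted sum alone.
- ***Enrich at IA#4*.** The first weight is w23 = n23/n_Primary. The second is (1 − w23) times its share of the remaining subjects. The third is (1 − w13) times its share. The footnote to the row says: "The denominator changes as we have the new sample size. The planned sample size is covered in" w23 and (1 − w23).
- ***Enrich at IA#2*.** One denominator reads n_Primary − 22; the neighbouring cell has n_Primary − n22.

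**The concern.** An inverse-normal combination test keeps its level only if the weights are fixed beforehand and sum to 1, and if the combined Z is converted to a p-value before it meets a threshold. The IA#3 rows fail the second condition as printed, and the IA#4 row fails the first unless w13 happens to equal w23. The section says that the family-wise error is strictly held below 20%, and this procedure is the SAP's only inference on the key clinical endpoints that adjusts for the adaptations. A correction made after unblinding, however obvious, could be challenged because it changes the result. Separately, a two-sided decision with no stated direction leaves open what makes an endpoint succeed, and that event releases alpha to the other endpoints.

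**Working it through.** **Inputs.** Section 5.2.3.2: n22 ≈ 36, n23 ≈ 75, n24 ≈ 150, n13 ≈ 144; n_Primary = 225 (clinical) and 294 (viral load). Section 5.6: total Cohort 2 sizes of 150 to 300. A total of 150 means no increase, so enrichment at IA#4 can arise only at 180 to 300.

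**The plan's own figures.** (150 + 300)/2 = 225 and 20%/3 = 6.667%. Both reproduce. The IA#3 weights are 75/225 + 150/225 = 1.

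**IA#3 rows.** With both stage p-values at 0.10, the printed expression is (√0.3333 + √0.6667) × 1.2816 = 1.394 × 1.2816 = 1.79. The two-sided conversion then gives 2 × min{1.79, −0.79} = −1.57. With the wrapper restored, p = 1 − Φ(1.79) = 0.037. Taken literally, the rule 2 × min{Z, 1 − Z} ≤ 0.20 rejects when Z ≤ 0.1 or Z ≥ 0.9. Under the null that has probability Φ(0.1) + 1 − Φ(0.9) = 0.540 + 0.184 = 0.724. At 6.667% it is 0.680.

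**IA#4 row.** Let N be the re-planned total and b = (N − 150)/(N − 75). The printed weights sum to

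w23 + (1 − w23)(1 − b) + (1 − w13)b = 1 − b(w13 − w23),

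which is 1 only if w13 = w23. Here w23 = 75/225 = 0.333. The clinical table has no w13. The only weight with that index in the section is in the viral load table, (144 + 75)/294 = 0.745. With that value, and true one-sided size 1 − Φ(z/√sum):

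| N | Sum of weights | Size at nominal 10% | Size at nominal 3.33% (first Holm step) |
|---|---|---|---|
| 180 | 0.882 | 8.6% | 2.6% |
| 210 | 0.817 | 7.8% | 2.1% |
| 240 | 0.776 | 7.3% | 1.9% |
| 270 | 0.747 | 6.9% | 1.7% |
| 300 | 0.726 | 6.6% | 1.6% |

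At N = 300 the three weights are 0.333 + 0.222 + 0.170; with w23 in the third they are 0.333 + 0.222 + 0.444 = 1.

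*Power at N = 300*, assuming the same effect in every stage and information proportional to n (75, 75, 150). The correct weights give Σ√(w·n) = 5.00 + 4.08 + 8.16 = 17.25. For 80% power at 10% one-sided the mean of the statistic is 1.2816 + 0.8416 = 2.123, so the effect per √n is 0.1231. The printed weights give 5.00 + 4.08 + 5.05 = 14.13, mean 1.740, SD √0.7256 = 0.852. Power is Φ((1.740 − 1.2816)/0.852) = 70%. The same steps at N = 180 give 77%.

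*Alternative reading of w13.* If w13 = 144/225 = 0.64, the sum is 0.912 at N = 180 and 0.796 at N = 300, with sizes 9.0% and 7.5%.

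**IA#2 row.** Taken literally: 0.1600 + 0.1614 + 0.6667 = 0.988, size 9.9% instead of 10%. With n22 the sum is 1.

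**Direction.** A one-sided p of 0.97 gives 2 × 0.03 = 0.06, below 0.0667. Under the null, half of the 20% (10%) lies in the wrong direction.

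**The case against.** The intent can be recovered from the page. The footnote gives w23; the other clinical blocks and the viral load IA#3 rows carry 1 − Φ; and a p-value of 1.79 would be noticed when programmed. Sections 5.1.1 and 5.2.3.2 call this a secondary analysis approach in an exploratory study, and the futility rules in Section 5.6 do not use these final p-values. The faulty rows are mutually exclusive scenarios, and the IA#4 row also needs an enlarged Cohort 2. All of that stands and limits the consequences. It does not make the printed formulas right: they are the pre-specified ones, and Section 5.6 has its own enrichment rule at IA#3, so that branch can occur.

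A reader might also infer that the two-sided conversion makes harm count as success. The document does not support that. The conversion is the standard two-sided p-value, it matches the 10% one-sided test exactly when the effect is beneficial, and nowhere does the SAP call a harmful result a success. What is missing is an explicit direction condition.

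Nor does the IA#4 slip inflate Type I error: under either reading of w13 tried above, the test is conservative.

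**Conclusion.** Two formulas are wrong as printed. The IA#3 rows do not yield a p-value; this needs no assumption, but the 72% rejection rate arises only if the rule is coded literally. The IA#4 weights do not sum to 1 unless w13 = w23. The size of that error (sum 0.882 to 0.726, one-sided size 8.6% to 6.6%, power about 77% to 70% instead of 80%) rests on taking w13 from the viral load table, and the power figures also on a constant effect across stages. The IA#2 denominator is negligible and may be a fault of text extraction. The missing direction condition is a gap in wording. The combination method itself is sound, and the unadjusted primary viral load analysis is untouched. The corrections matter because they fix the only adaptation-adjusted inference on the key clinical endpoints.

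**What to change.** In Section 5.2.3.2, clinical course table:

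1. *Enrich at IA#3*: enclose both final p-value expressions in 1 − Φ(...).
2. *Enrich at IA#4*: replace w13 by w23 in the third weight.
3. *Enrich at IA#2*: check the source and, if needed, write n_Primary − n22.
4. Keep the two-sided conversion, but state that an endpoint succeeds in the Holm procedure only if the effect is in the beneficial direction (reported one-sided p below 0.5). Equivalently, compare the one-sided p with half the two-sided level: 10% overall, 3.33% at the first step.

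The cost is a few lines of SAP text and a check of the analysis code, with no new data. The changes should be dated before the unblinded analysis that uses them.
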